5.1 Design overview

This is a non-randomized, open-label, multicenter, Phase II study to evaluate the efficacy and safety of intravenous anetumab ravtansine (BAY 94-9343), an anti-mesothelin antibody drug conjugate, in pretreated mesothelin-expressing advanced pancreatic cancer.

At the time of the start of study treatment, the patients will have pretreated advanced pancreatic cancer that also overexpresses mesothelin as determined by immunohistochemistry (IHC). Mesothelin testing will be performed centrally.

A maximum of 30 patients will be enrolled in a minimax, Simon 2-stage design with a single early stopping rule for lack of efficacy. The target population is those patients with pancreatic cancer who have failed an earlier treatment. All patients will be treated with an anti-mesothelin immuno-conjugate, in this single arm, non-randomized trial and all patients treated with at least one dose of Anetumab will be included. The endpoint is any response using the RECIST 1.1 criteria.

The minimax, Simon 2-stage design testing 5% null hypothesis versus a 21% alternative requires a maximum of 30 patients. If there are no patients exhibiting any response among the first 20, which indicates a response rate less than 5%, then the trial will terminate early. If there is at least one response among the first 20 (indicating response rate of at least 5%) then the trial will accrue an additional 10 patients for a maximum of 30. Four or more responses out of 30 will reject the null hypothesis in favor of the 21% response alternative. These

criteria have significance level (alpha) 0.1 and power 90%. The probability of stopping early is 36% if the response rate is 5% or lower. The expected sample size is 26.4.

The start of the treatment period is defined by first administration of study drug (anetumab ravtansine). Patients will receive anetumab ravtansine IV infusion at a dose of 6.5 mg/kg (recommended Phase II dose [RPIID]) on Day 1 of a 21-day cycle. Treatment will be continued until death or occurrence of PD as defined by Response Evaluation Criteria in Solid Tumors (RECIST) v1.1 and assessed by blinded radiology review, or clinical progression, or until another criterion for withdrawal from the study is met.

Patients who discontinue study treatment for any reason other than confirmed radiological PD will be followed for progression during active follow-up (which includes the safety follow-up period) until confirmed PD for this patient is observed.

All patients who end study treatment for any reason will be followed for OS and the start of any new anti-cancer treatment every 3 months during the long-term follow-up period until data maturation for the OS final analysis is reached, or until death, consent withdrawal or end of study, whichever occurs first.

Primary efficacy will be assessed based on radiological tumor evaluation by contrast-enhanced computed tomography (CT) or contrast-enhanced magnetic resonance imaging (MRI) of chest/abdomen/pelvis. During treatment as well as active follow-up, tumor imaging will be performed with the same modality to the extent possible, every 6 weeks during the first 6 months after the start of study treatment, every 9 weeks until the end of year 2, and every 12 weeks thereafter until RECIST confirmed radiological disease progression or end of study.

Safety evaluations will be done at full screening, at each clinic visit during the treatment period, and at the safety follow-up visit. The National Cancer Institute's Common Terminology Criteria for Adverse Events (NCI-CTCAE) version 4.03 will be used to grade severity of adverse events (AEs).

Patients will be contacted to assess survival status every 3 months during long-term follow-up. In addition, extra survival sweep contacts will be conducted at the time of PFS final analysis and prior to OS final analysis to ensure that long-term follow-up data is current.

5.2 Primary variable

The primary variable of this study is response rate as measured per RECIST 1.1 criteria.

6. Study population

6.1 Inclusion criteria

Patients eligible for inclusion into the study must meet the following inclusion criteria.

6.1.1 Eligibility criteria for prescreening

Prescreening can be performed without evidence of disease progression after the initial treatment at the investigator's discretion.

1. Written informed consent for prescreening.

2. Unresectable locally advanced or metastatic pancreatic cancer, confirmed by histology.
3. At least one but not more than two prior chemotherapy regimens with progression or documented intolerance (neoadjuvant or adjuvant chemotherapy would not be counted as a line of therapy. If prior radiation, measurable lesion outside radiation portal).
4. Availability of archival or fresh tissue for testing of mesothelin expression level.
Note: Archival tissue is preferred and fresh biopsy should only be obtained if no archival tissue is available and if in the investigator's judgement, there is no additional risk for the patient's safety. Patients with a sarcomatoid histology are not expected to have mesothelin overexpression and should not enter prescreening.
5. Age \geq 18 years.
6. Life expectancy of at least 3 months.
7. No prior treatment with anetumab ravtansine (or any other mesothelin-based therapy)

Besides these basic criteria, any criterion as outlined below under inclusion eligibility criteria for the full study and exclusion criteria already known to prohibiting the patient's participation in the study should be considered. No study-related procedures should be performed which are not covered by the prescreening ICF.

6.1.2 Eligibility criteria for full study

The following inclusion criteria must be met at the time of screening, prior to the start of study drug, unless otherwise specified.

1. Written informed consent for full study.
2. Histological documentation of overexpressing mesothelin at the moderate (2+) or stronger (3+) level in at least 30% of tumor cells as determined by IHC.
3. Unresectable locally advanced or metastatic pancreatic cancer
4. At least one but not more than two prior chemotherapy regimens with progression or documented intolerance (neoadjuvant or adjuvant chemotherapy would not be counted as a line of therapy. If prior radiation, measurable lesion outside radiation portal).
5. Patients must have at least 1 measurable lesion according to RECIST v 1.1 (specified in Section 9.4.1).
6. ECOG PS of 0 or 1 (specified in Appendix 16.1).
7. Life expectancy of at least 3 months.
8. Adequate bone marrow, liver and renal function as assessed by the following laboratory requirements conducted within 7 days before starting study treatment:
 - Total bilirubin \leq 1.5 x the upper limit of normal (ULN). Documented Gilbert syndrome is allowed if total bilirubin is mildly elevated ($<$ 6 mg/dL).
 - ALT and AST \leq 2.5 x ULN (\leq 5 x ULN for patients with liver involvement of their cancer).
 - ALP limit \leq 2.5 x ULN (\leq 5 x ULN for patients with liver involvement of their cancer).

- Extent of baseline tumor burden will not interfere with causal assessment of treatment-emergent hepatotoxicity, at the investigator's discretion.
- Amylase and lipase $\leq 1.5 \times \text{ULN}$.
- Glomerular filtration rate (GFR) $\geq 30 \text{ mL/min/1.73 m}^2$ according to the Modification of Diet in Renal Disease (MDRD) abbreviated formula (see Appendix 16.6).
- Adequate coagulation, as assessed by the following laboratory test results:
 - International normalized ratio (INR) or prothrombin time (PT) $\leq 1.5 \times \text{ULN}$ (CTCAE Grade ≤ 1).
 - Partial thromboplastin time (PTT) or activated PTT (aPTT) $\leq 1.5 \times \text{ULN}$ (CTCAE Grade ≤ 1).

Note: Patients on stable dose of anti-coagulation therapy will be allowed to participate if they have no sign of bleeding or clotting and INR / PT and PTT / aPTT test results are compatible with the acceptable benefit-risk ratio at the investigator's discretion (see Section 8.1).

- Platelet count $\geq 75,000/\text{mm}^3$, without platelet transfusion within 3 weeks before the start of study treatment (see Section 8.1).
- Hemoglobin (Hb) $\geq 8 \text{ g/dL}$,

Note: Patients receiving chronic low-dose erythropoietin for chronic renal failure are allowed provided no dose adjustment is undertaken within 6 weeks before signing consent for full study and until safety follow-up visit and provided that they fulfill conditions of eligibility criteria (see also exclusion criterion number 18).

- Absolute neutrophil count (ANC) $\geq 1000/\text{mm}^3$

9. Left ventricular ejection fraction (LVEF) $\geq 50\%$ or the lower limit of normal (LLN) according to local institution ranges of normality.

6.2 Exclusion criteria

Patients who meet the following criteria at the time of full screening and on C1D1 will be excluded:

1. Previous assignment to treatment during this study. Patients permanently withdrawn from study participation will not be allowed to re-enter the study.
2. Previous (within 5 drug half-lives – if drug half-life in subjects is known – or 28 days, whichever is shorter, before the start of study treatment) or concomitant participation in another clinical study with investigational medicinal product(s) (IMP[s]).
3. Patients with corneal epitheliopathy or any eye disorder that may predispose the patients to this condition at the discretion of the investigator.
4. Previous or concurrent cancer that is distinct in primary site or histology within 5 years. Exceptions: curatively treated
 - Cervical cancer *in situ*.

- Non-melanoma skin cancer.
 - Superficial bladder tumors (Non-invasive tumor [Ta], Carcinoma *in situ* [Tis] and Tumor invades lamina propria [T1]).
5. Major surgery, open biopsy or significant traumatic injury within 28 days before the start of study treatment.
 6. Pregnant or breast-feeding patients. WOCBP must have a serum pregnancy test performed a maximum of 7 days before the start of study treatment, and a negative result must be documented before the start of study treatment.
 7. Pre-existing cardiac conditions as outlined below:
 - Congestive heart failure \geq New York Heart Association (NYHA) class 2 (specified in Appendix 16.2).
 - Unstable angina (angina symptoms at rest), new-onset angina (begun within the last 3 months). Myocardial infarction less than 6 months before the start of study treatment.
 - Cardiac arrhythmias requiring anti-arrhythmic therapy (beta blockers or digoxin are permitted).
 8. Clinically significant uncontrolled hypertension (systolic blood pressure $>$ 150 mmHg or diastolic pressure $>$ 90 mmHg despite optimal medical management).
 9. Arterial thrombotic or embolic events such as cerebrovascular accident (including transient ischemic attacks), or venous pulmonary embolism within 6 months before the start of study treatment; venous thrombotic events such as deep vein thrombosis within 3 months before the start of study treatment.
 10. Ongoing or active infection (bacterial, fungal, or viral) of NCI-CTCAE version 4.03 Grade $>$ 2.
 11. Known history of human immunodeficiency virus (HIV) infection.
 12. Known history of chronic hepatitis B or C.
 13. Patients with seizure disorder requiring medication.
 14. Symptomatic brain metastases or meningeal tumors or other uncontrolled metastases in the central nervous system (CNS) unless the patient
 - Is $>$ 6 months from definitive therapy,
 - Has a negative imaging study within 4 weeks before study entry (ICF signature for full study) and
 - Is clinically stable with respect to the tumor at the time of study entry.
 15. History of organ allograft, stem cells or bone marrow transplant.
 16. Patients with evidence or history of bleeding diathesis. Any hemorrhage or bleeding event \geq CTCAE Grade 3 within 4 weeks before the start of study treatment.
 17. Non-healing wound, ulcer, or bone fracture.
 18. Renal failure requiring peritoneal dialysis or hemodialysis.

19. Known hypersensitivity to anetumab ravtansine, study drug classes or excipients in the formulation.
20. Any illness or medical conditions that are unstable or could jeopardize the safety of the patient and his/her compliance in the study.
21. Unresolved toxicity higher than NCI-CTCAE version 4.03 Grade 1 attributed to any prior therapy/procedure excluding anemia or neuropathy Grade 2 (see Section 6.1.2, inclusion criterion 8) and alopecia of any Grade.
22. Any prohibited prior or concomitant therapy (see **Table 2-8** in Section 8.1).

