IB	Investigator's brochure
ICF	Informed consent form
ICH	International Conference on Harmonization
IDS	Investigational Drug Service
IEC	Independent Ethics Committee
IgG1	Immunoglobulin G subclass 1
IHC	Immunohistochemistry
ILD	Interstitial lung disease
IM	Immunogenicity
IMP	Investigational medicinal product
INR	International normalized ratio
IOP	Intraocular pressure
IRB	Institutional Review Board
ITT	Intent-to-treat (set)
IUD	Intrauterine device
IUS	Intrauterine hormone-releasing system
IV	Intravenous
kg	Kilogram(s)
LDH	Lactic dehydrogenase
LLN	Lower limit of normal
LPLV	Last patient last visit
LVEF	Left ventricular ejection fraction
m ²	Square meter(s)
MCU	Multi-Center Unit
MD	Doctor of Medicine

Clinical Study Protocol

19-September-2018

BAY 94-9343 (Anetumab in Pancreatic Cancer)

Version 4.0

Page: 12 of 77

MDRD	Modification of Diet in Renal Disease
MedDRA	Medical Dictionary for Regulatory Activities
mg	Milligram(s)
Min	Minute(s)
miRNA	Micro ribonucleic acid
mL	Milliliter(s)
mm ³	Cubic millimeter(s)
mmHg	Millimeter of mercury
MoA	Mechanism of action
mRECIST	Modified Response Evaluation Criteria in Solid Tumors
MRI	Magnetic resonance imaging
MTD	Maximum tolerated dose
MUGA	Multiple gated acquisition
N	Number of patients
n	Number of non-missing values
N HCl	Normal hydrochloric acid
NC	No change
NCCN	National Comprehensive Cancer Network
NCI-CTCAE	National Cancer Institute's Common Terminology Criteria for Adverse Events
NE	Not evaluated
NGS	Next generation sequencing
NYHA	New York Heart Association
ORR	Objective response rate
OS	Overall survival
PD	Progressive disease
PET	Positron emission tomography
PFS	Progression-free survival
PFT	Pulmonary function test
P-gp	Permeability glycoprotein
PhD	Doctor of Philosophy
PI	Principal Investigator
PK(s)	Pharmacokinetic(s)
PR	Partial response
PT	Prothrombin time
PTT	Partial thromboplastin time
Q3W	Every 3 weeks
QA	Quality assurance
QW	Once weekly
RECIST	Response Evaluation Criteria in Solid Tumors
RNA	Ribonucleic acid
RPIID	Recommended Phase II dose
RR	Respiratory rate
RT	Radiotherapy
SAE	Serious adverse event

Clinical Study Protocol

19-September-2018

BAY 94-9343 (Anetumab in Pancreatic Cancer)

Version 4.0

Page: 13 of 77

SAF	Safety set
SAP	Statistical Analysis Plan
SAS	Statistical Analysis Software
SD	Stable disease
SoC	Standard of care
SPDB	N-succinimidyl 4-(2-pyridyldithio)butyrate (reducible disulfide linker)
SPK	Superficial punctate keratitis
SQR RT	Square root ($\sqrt{\quad}$)

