3.1 Background

Mesothelin is a membrane associated differentiation antigen present on normal mesothelial cells and overexpressed in a vast majority of ductal pancreatic adenocarcinomas, mesotheliomas, and adenocarcinomas of the ovary. The biological function of mesothelin remains unknown and mesothelin-deficient mice have no obvious phenotype of defect. Mesothelin is an internalizing antigen and shows a restricted expression profile in normal tissue making it an excellent target for antibody directed cytotoxic drug delivery.

BAY 94-9343, anetumab ravnansine, is an antibody-drug conjugate consisting of a fully human IgG1 antibody (MF-T, BAY 86-1903) directed at the mesothelin antigen and conjugated to a synthetic cytotoxic anticancer agent, maytansine derivative (DM4, BAY 1006640) as toxophore through a reducible disulfide linker (SPDB). Preclinical efforts have shown specific effects on mesothelin positive cell lines and in xenograft models including activity in pancreatic BxPC3 xenograft model. Toxicology studies showed a number of important signals but specifically skin toxicity.

Human phase 1 and PK studies were performed showing terminal phase half-life values of the ADC and Total Antibody were approximately 5.5 to 6 days. Plasma DM4 and DM4-Me concentrations declined with a half-life of approximately 3 days and 5.5 days at the MTD. DM4-Me pharmacokinetics exhibited moderate to high variability and exposure increased in a substantially more than dose proportional manner in the dose range studied.

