- Patient starts treatment with any other anti-cancer therapy or any other prohibited medication as per Section 8.1.
- Positive serum β -HCG test consistent with pregnancy. Pregnancy should be reported along the same timelines as an SAE.
- Use of illicit drugs or other substances that may, in the opinion of the investigator or his designated associate(s), have a reasonable chance of contributing to toxicity or otherwise confound the results.
- Development of any intercurrent illness or situation which may, in the judgment of the investigator, affect assessments of clinical status and study endpoints to a relevant degree.
- Lost to follow-up.
- Death.

Patients must be withdrawn from **treatment with anetumab ravtansine** if any of the following occurs:

- CTCAE Grade 4 non-hematological AE and Bayer Grade 4 corneal toxicity (see Table 2-6) (except at the investigator's discretion in case of certain Grade 4 abnormality of laboratory assessments, such as abnormal laboratory assessments without corresponding clinical symptoms, or abnormal laboratory assessments that can be easily clinically managed).
- If any type of TEAE requiring dose modification does not resolve to Grade ≤ 1 (or Hb ≥ 8 g/dL in case of anemia) within 6 weeks after the last dose of anetumab ravtansine.
- Delay in anetumab ravtansine administration of 3 weeks (max. 6 weeks between 2 infusions of study drug).
- TEAE requiring dose reduction when already at the 4.5 mg/kg Q3W dose level (minimum dose).
- More than 2 dose reductions required due to a TEAE.

AE = Adverse event; β -HCG = β subunit of human chorionic gonadotropin; CTCAE = Common Terminology Criteria for Adverse Events; Hb = Hemoglobin; RECIST = Response Evaluation Criteria in Solid Tumors; PD = Progressive disease; Q3W = Every 3 weeks; SAE = Serious adverse event; TEAE = Treatment-emergent adverse event

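### The protocol text requires no contraception, during or after treatment, from women of childbearing potential or from men given a cytotoxic antibody-drug conjugate

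*Combined protocol and SAP*

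**What the plan says.** Section 3.1 describes an antibody "conjugated to a synthetic cytotoxic anticancer agent, maytansine derivative".

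Eligibility is set in three numbered lists:

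- Section 6.1.1 (prescreening) has 7 items. The last is "No prior treatment with anetumab ravtansine (or any other mesothelin-based therapy".
- Section 6.1.2 (full study) opens with "The following inclusion criteria must be met at the time of screening, prior to the start of study drug" and has 9 items, ending with left ventricular ejection fraction.
- Section 6.2 (exclusions) has 22 items, ending with prohibited therapies. Item 6 excludes pregnant and breast-feeding patients and adds that "WOCBP must have a serum pregnancy test performed a maximum of 7 days before the start of study treatment", with a negative result on file before dosing.

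After entry, Sections 9.2.2 and 9.5.3.1 repeat the serum test at least every 6 weeks for women of childbearing potential. Section 9.2.3.2 places it on odd cycles. Under Section 6.3.2 (Figure 2-1) a positive test ends study treatment, and "Pregnancy should be reported along the same timelines as an SAE". Section 9.5.2 requires the investigator to report a patient's pregnancy to the sponsor and to follow mother and child, and asks for similar information on partners' pregnancies. Section 9.5.1.5 (reporting of serious adverse events) lists which pregnancies go to the drug supplier.

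**The concern.** For a cytotoxic drug one expects a rule that fertile participants use contraception during treatment and for a stated time afterwards. Here every provision either screens out an existing pregnancy or responds to one that has occurred.

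The protocol itself treats pregnancy as serious: it is a reason to exclude, to stop treatment and to report on serious-adverse-event timelines. Section 12 names teratogenicity and reproduction toxicity findings from animal studies among possible reasons to close the study. What is at stake is avoidable exposure of a fetus, through a female patient or possibly through a male patient. This is a participant-safety point and does not touch the statistical design.

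**Working it through.** The claim is about missing text, so there is no planned figure to reproduce. The check sets each relevant provision beside the question of whether it acts before conception.

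| Provision | What it does | Prevents conception on study? |
|---|---|---|
| 6.1.1, items 1-7 | Consent, disease, prior therapy, tissue, age, life expectancy, no earlier mesothelin-based therapy | No |
| 6.1.2, items 1-9 | Consent, mesothelin, disease, prior therapy, measurable lesion, performance status, life expectancy, laboratory values, cardiac function | No |
| 6.2, item 6 | Excludes current pregnancy and breast-feeding; one test before dosing | No |
| 6.2, other items to 22 | None concerns fertility | No |
| 9.2.2, 9.2.3.2, 9.2.5.1, 9.5.3.1 | Repeat testing of women | No; detects afterwards |
| 6.3.2, Figure 2-1 | Stops treatment on a positive test | No; acts afterwards |
| 9.5.1.5, 9.5.2 | Report and follow up pregnancies | No; act afterwards |

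The three lists are numbered without gaps and show no blacked-out text, so removed text does not explain the absence.

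**How far testing can stand in for prevention**

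- Inputs: infusions every 3 weeks (Section 7.3.1); tests at least every 6 weeks, on odd cycles (Section 9.2.3.2); baseline test up to 7 days before treatment (Section 6.2).
- Infusions per required test: 6 / 3 = 2.
- On the minimum schedule, infusions fall at week 0 (cycle 1), week 3 (cycle 2) and week 6 (cycle 3). After the baseline test, the next required test is at cycle 3.
- Greatest age of the last required test at the cycle 2 infusion: 7 + 21 = 28 days, before visit windows.

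A woman who conceives after a test can thus receive the next even-cycle infusion before another test is due. Testing limits continued dosing in pregnancy but does not rule out all dosing.

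**Men.** No provision acts before a partner's pregnancy is reported.

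**After the last dose.** Section 8.2 says that the conjugate and its metabolites may be detectable for several weeks. It says so about interactions with later therapy, but it is enough to show that exposure does not end with the last infusion. The protocol text sets no post-treatment contraception period.

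**The case against.** The strongest objection is that the instruction may sit elsewhere. Section 13.5.2 says that the full-study consent form summarizes all relevant information, and Section 9.5.1.5 (expected adverse events) makes the investigator's brochure the safety reference. Neither document was available. The opening part of the Section 9.1 schedule was also missing from the text I had, though a schedule of assessments is an unlikely home for such a rule. This objection stands to the extent that one cannot say patients receive no contraception advice. It does not remove the gap: Section 13.4 requires strict adherence to the protocol, and advice in a consent form is not a criterion that a site checks before dosing.

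It is also fair that repeat testing with mandatory withdrawal is a real control. It shortens exposure, within the limits shown above.

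Three stronger readings are tempting, and the documents do not support them:

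- **A clause was lost in drafting.** The abbreviation list defines "Intrauterine hormone-releasing system" and intrauterine device, and neither is used in the text. But that list holds many unused terms, such as CYP2D6, NCCN and QW, so two more show little.
- **The half-lives imply a 30-day minimum.** Section 3.1 reports that "terminal phase half-life values of the ADC and Total Antibody were approximately 5.5 to 6 days" and that DM4 and its methyl metabolite "declined with a half-life of approximately 3 days and 5.5 days at the MTD". Five half-lives of the conjugate are 5 x 5.5 = 27.5 to 5 x 6 = 30 days. Nothing in the documents makes five half-lives a contraception rule, and they contain no reproductive-risk data. Section 3.1 describes the metabolite's kinetics as moderately to highly variable, and circulating levels do not measure risk through a male patient. Printing 30 days could anchor too short a period.
- **Partner pregnancies conceived more than two weeks after the last dose go unreported.** The two-week limit in Section 9.5.1.5 concerns notice to the supplier. It stands beside a separate limb for exposure at conception, and Section 9.5.2 sets no time limit for partner pregnancies reported to the sponsor.

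**Conclusion.** The point holds as an omission from the protocol text. The protocol excludes, tests for, withdraws on and reports pregnancy, but nowhere requires contraception from women of childbearing potential or from men with partners of childbearing potential, during or after treatment.

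The likely number of events is small: at most 30 patients are treated, and the documents do not say how many would be fertile. The two-stage design, the response rate and the other planned analyses are unaffected. An amendment is still worthwhile because the harm is serious and preventable and the remedy is cheap.

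The conclusion assumes that no contraception rule sits in the part of the schedule I could not see. It makes no claim about the consent form, the brochure, or how long contraception needs to last.

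**What to change.** Add a tenth inclusion criterion to Section 6.1.2:

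> 10. Women of childbearing potential, and men who are not surgically sterile and have partners of childbearing potential, agree to use highly effective contraception from signing of the full-study consent, during treatment, and after the last dose for the period specified in the current investigator's brochure.

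Do not add a numeric minimum derived from the half-lives. Check the brochure and consent form first: if they already give instructions, the amendment only aligns the protocol with them.

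As an optional alignment, replace the two-week partner-conception limit in Section 9.5.1.5 (reporting of serious adverse events) with the same post-treatment contraception period. Leave Section 9.5.2 without a time limit for partners.

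The cost is one protocol amendment, consent wording if it is not already present, and one more eligibility item to document. No test or visit is added.
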